## 11.5. VITAL SIGNS

Vital signs (systolic blood pressure, diastolic blood pressure, pulse rate and respiratory rate) are assessed at all visits at the following time points: within 30 minutes before each infusion, 15 to 30 minutes after the start of each infusion, 15 to 30 minutes after the start of each infusion, and 15 to 30 minutes after the start of any change in the infusion rate. In any case where the change in infusion rate is sooner than a 15 minute interval, vital signs should be measured prior to the change.

Body temperature is collected at all visits during the treatment period within 30 minutes before each infusion only.

For vital sign parameters, absolute values and changes from baseline will be presented for each study visit and where available at the time points 30 minutes before each infusion, 15 to 30 minutes after the start of each infusion, 15 to 30 minutes after the start of any change in the infusion rate and 15 to 30 minutes after the end of each infusion using summary descriptive statistics.

In addition changes from infusion start (30 minutes before each infusion) will be presented for each infusion at the time points 15 to 30 minutes after the start of each infusion, 15 to 30 minutes after the start of any change in the infusion rate and 15 to 30 minutes after the end of each infusion using summary descriptive statistics.

Absolute values and changes from baseline will be presented for each scheduled study visit for body temperature and weight.

For the definition of baseline value refer to Section 6.2.

All data will be listed.

## 11.6. PHYSICAL EXAMINATION

For each subject, a complete physical examination is performed at each visit as described in the Flowchart, Section 3.8.. The physical examination includes an inspection of general appearance, skin, neck (including thyroid), eyes, ears, nose, throat, heart, lungs, abdomen, lymph nodes, vascular system, extremities, musculo-skeletal system, and nervous system. Clinical findings and existing diseases at screening are to be documented as medical history. A new appearance of an abnormal finding or worsening of a concomitant disease that is considered clinically significant and occurs after signature of informed consent/assent must be documented as an AE.

• Body weight is measured in kilograms (kg).

• Body height is measured in cm once at the screening visit for the purpose of calculation of body mass index.

The physical examination is followed-up with a verbal exchange (face-to-face) between the subject and the investigator 1 hour after the end of each infusion, and a verbal exchange (by telephone) 24 and 72 hours after the end of each infusion.

At each exchange, the subject reports any changes since the physical examination performed before the BT595 infusion. Any new physical examination findings are documented as AEs.

The number and percentage of subjects with assessments of normal, abnormal NCS, abnormal CS or Not Done at all scheduled visits (prior to infusion during the treatment period) will be displayed in a summary table for each body system.

The number and proportion of subjects with at least 1 CS abnormal value and the number of CS abnormal values will be summarized by the different categories.

Changes over time will be described by means of "shift-tables", comparing the post baseline values versus baseline value. Percentages will be calculated from the number of subjects with the given result at baseline. For the definition of baseline value refer to Section 6.2.

All data will be listed.

## 11.7. OTHER SAFETY

## 11.7.1. Intravascular Hemolysis

The intravascular hemolysis tests are performed at screening (initial visit) and the closing (follow-up) visit only, unless further tests are required. Tests for the detection of intravascular hemolysis consist of a direct antiglobulin test (Coombs test) and the measurement of serum haptoglobin, plasma-free hemoglobin, and urine hemosiderin.

For the first 10 patients, additional data are available for their first 2 infusions (V2 and V3) on direct antiglobulin test (Coombs test) and the test of serum haptoglobin at the time points V3 and V4, as those data had been required by the Data and Safety Monitoring Board.

If the Coombs test result is positive, the test will be repeated and red blood cell count, hematocrit, hemoglobin (including plasma-free), serum haptoglobin, bilirubin (total, direct, and indirect), lactate dehydrogenase, and urine hemosiderin tests will be performed within 2 to 5 days.

If the hemoglobin level has dropped by  $\geq 2.0$  g/dL from the screening level in conjunction with both a drop in serum haptoglobin to below the lower limit of normal and a rise in serum lactate dehydrogenase from the screening level, this will suggest intravascular hemolysis, and a repeat urine dipstick, micro-urinalysis, and assessment of hemoglobin levels will be obtained within 72 hours of being informed of the drop in hemoglobin levels.

Intravascular hemolysis laboratory assessments (Coombs test, serum haptoglobin, plasmafree hemoglobin, and urine hemosiderin) will be summarized by the number and percentage of subjects with the given results at each scheduled visit. In case of positive Coombs test results, further evaluations and/or time points will be included in the summaries. In case of intravascular hemolysis (drop in hemoglobin level by ≥2.0 g/dL and drop in serum haptoglobin to below the lower limit of normal and a rise in serum lactate dehydrogenase compared to the screening level), or in case of intravascular hemolysis reported as AESI in the eCRF, narratives will be presented for those subjects meeting the conditions.

In addition, summaries will be presented in case of drop in hemoglobin level  $\geq$  1.0 g/dL in conjunction with a drop in serum haptoglobin to below the lower limit of normal and rise of serum lactate dehydrogenase compared to screening level.

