The intravascular hemolysis tests will be performed at screening (initial visit) and the closing (follow-up) visit only, unless further tests are required. Tests for the detection of intravascular hemolysis will consist of a direct antiglobulin test (Coombs' test; approximately 7 mL blood sample) and the measurement of serum haptoglobin, plasma-free hemoglobin, and urine hemosiderin. If the Coombs' test result is positive, the test will be repeated and red blood cell count, hematocrit, hemoglobin, serum haptoglobin, bilirubin (total, direct, and indirect), lactate dehydrogenase, and urine hemosiderin tests will be performed within 2 to 5 days. If the hemoglobin level has dropped by ≥ 2.0 g/dL from the screening level, in conjunction with both a drop in serum haptoglobin to below the lower limit of normal and a rise in serum lactate dehydrogenase from the screening level, this will suggest intravascular hemolysis, and a repeat urine dipstick, micro-urinalysis, and assessment of hemoglobin levels.

For the first 10 patients and their first 2 infusions (V2 and V3) the results of the direct antiglobulin test (Coombs test) and the test of serum haptoglobin at the time points V3 and V4 are required as a prerequisite for the decision of the Data and Safety Monitoring Board. For those 10 patients approximately 7 mL of additional blood will be taken for each of the two visits (V3 + V4).

Note: the approximate blood sample volumes are estimated, and as the samples will be tested by local laboratories, volumes may differ from the approximate blood volumes detailed.

Virus Serology

The immunological status of viral infections will be assessed at screening (initial visit) for:

- HIV (anti-HIV1 and anti-HIV2)
- hepatitis B (total hepatitis B core antibody [anti-HBc], hepatitis B surface antibody [anti-HBs], hepatitis B surface antigen [HBsAg])
- hepatitis C (anti-HCV)

Pregnancy Test

In females of child-bearing potential (i.e., female subjects ≥12 years or with presence of menstruation at screening), a pregnancy human chorionic gonadotropin test in serum will be performed at screening (initial visit). Urine pregnancy dipstick tests will be performed at other time points in the clinical study as specified in Section III, Flowchart of Study.

The serum sample will be analyzed by the local laboratory using standard assay methods and the urine dipstick test will be analyzed at the study site.

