- All AEs that result in a subject's withdrawal from the study
- Overdose
- Pregnancy
- Adverse Events Leading to Subject's Withdrawal from the Clinical Study

An AE, serious or nonserious, resulting in a subject's withdrawal from the clinical study, i.e. permanent treatment discontinuation. Reporting requirements by the investigator are detailed in Appendix 2.

Mandatory Adverse Event Stopping Rules

Subjects have to be withdrawn if any of the following AEs occur:

- Thromboembolic events (such as stroke, myocardial infarction, lung embolism)
- Hemolysis •

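### The laboratory hemolysis criteria in SAP 11.7.1 need a haptoglobin value that is scheduled at very few treatment visits, and the SAP does not separate subjects who could not be evaluated from those who were negative

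*SAP*

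**What the plan says.** Schedule. SAP 11.7.1: "The intravascular hemolysis tests are performed at screening (initial visit) and the closing (follow-up) visit only, unless further tests are required". Protocol 9.2.1.4 has the same general rule: "The intravascular hemolysis tests will be performed at screening (initial visit) and the closing (follow-up) visit only". Both documents make one exception. In Protocol 9.2.1.4, for the first 10 patients, "the results of the direct antiglobulin test (Coombs test) and the test of serum haptoglobin at the time points V3 and V4 are required" for the Data and Safety Monitoring Board. Protocol 9.4 identifies these patients as adults.

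Criteria. SAP 11.7.1 writes narratives when hemoglobin falls by at least 2.0 g/dL with a "drop in serum haptoglobin to below the lower limit of normal and a rise in serum lactate dehydrogenase compared to the screening level". It adds summaries for a fall of at least 1.0 g/dL, again "in conjunction with a drop in serum haptoglobin to below the lower limit of normal and rise of serum lactate dehydrogenase compared to screening level". All three parts must be present in each criterion.

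Other routes. Narratives are also triggered by an investigator report: "or in case of intravascular hemolysis reported as AESI in the eCRF, narratives will be presented for those subjects meeting the conditions". SAP 11.3 retrieves hemolysis as an adverse event of special interest (AESI), both by investigator assessment and by a standardised MedDRA query (SMQ). After a positive Coombs test, both documents call for a repeat and a panel that includes haptoglobin within 2 to 5 days, and SAP 11.7.1 brings those results into the summaries.

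Routine laboratory. Protocol 9.2.1.4, Table 1, lists hemoglobin and LDH but not haptoglobin. Protocol 7.1 takes the routine panel at every treatment visit.

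Tabulation. SAP 6.1 restricts summary tables to scheduled visits and time points; unscheduled data are only listed.

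**The concern.** Two of the three components are collected throughout treatment, but the third hardly at all. The only stated trigger for extra haptoglobin is a positive Coombs test, and Coombs has the same sparse schedule. Nothing makes a fall in hemoglobin or a rise in LDH prompt a haptoglobin test.

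SAP 11.7.1 does not say how to classify a subject with a qualifying hemoglobin drop and LDH rise but no haptoglobin value. As the criterion is written, that subject does not meet it and so looks the same as a subject who was tested and found negative. Haptoglobin ordered for a reason other than a positive Coombs test could also drop out of the summaries under SAP 6.1.

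Hemolysis is an AESI. It is also on the mandatory withdrawal list in Protocol 9.3.1 ("Subjects have to be withdrawn if any of the following AEs occur"), and positive hemolysis test results are a safety endpoint. If few or no subjects meet the laboratory criterion, the report should let a reader see how far that reflects absence of hemolysis and how far absence of a measurement.

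**Working it through.** **1. Visit counts.** Protocol 7.1 gives 17 treatment visits after baseline (3-week schedule) or 13 (4-week schedule). Check: (51 − 3)/3 + 1 = 17 and (52 − 4)/4 + 1 = 13; both agree. Adding the closing visit gives 18 or 14 post-baseline visits.

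**2. Scheduled haptoglobin after baseline.** V3 and V4 in the first 10 patients: 10 × 2 = 20 tests during treatment. Closing: one per subject, N tests.

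**3. Coverage.** Let k be 17 or 13 treatment visits, and N be 70 (planned enrolment) or 50 (minimum evaluable), with the first 10 patients among the N. Put all subjects on one schedule, to give the range, with no dropout.

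- Treatment visits with scheduled haptoglobin = 20/(N × k)
- Post-baseline visits with scheduled haptoglobin = (N + 20)/(N × (k + 1))

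| N | Schedule | Treatment visits | Including closing |
|---|---|---|---|
| 70 | 3-week | 20/1190 = 1.7% | 90/1260 = 7.1% |
| 70 | 4-week | 20/910 = 2.2% | 90/980 = 9.2% |
| 50 | 3-week | 20/850 = 2.4% | 70/900 = 7.8% |
| 50 | 4-week | 20/650 = 3.1% | 70/700 = 10.0% |

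**4. By subject.** Each of the first 10 patients has 3 evaluable post-baseline visits (V3, V4, closing): 3 of 18 or 3 of 14. Every other subject has 1 of 18 or 1 of 14. Subjects with no scheduled haptoglobin between screening and closing: 60/70 = 86%, or 40/50 = 80%.

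**5. Pediatric subjects.** Protocol 4.1 lets no child start until at least 10 adults have had two infusions, and Protocol 9.4 places the V3 and V4 tests in adults. No pediatric subject therefore has a scheduled haptoglobin test during treatment. At least 20 evaluable pediatric subjects are planned, and SAP 11 presents all safety parameters by age category.

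**6. Is the gap covered by another table?** SAP 11.4 plans counts of clinically significant abnormal values and shift tables against baseline. Neither shows hemoglobin falls of 1.0 or 2.0 g/dL, nor a fall jointly with an LDH rise.

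**The case against.** The strongest answer is that finding hemolysis does not depend on this criterion. Investigator-reported AESIs get narratives without a haptoglobin value, and the SMQ retrieves coded events separately. Protocol 9.2.1.4 requires clinically relevant out-of-range laboratory values to be recorded as adverse events, unless they are a sign of one already reported. The schedule allows further tests where required. Hemolysis leads to withdrawal, and withdrawn subjects should have the closing examinations, which include haptoglobin. All of this stands. These routes, however, mostly depend on someone first recognising a problem, whereas a laboratory criterion applied to every subject would not.

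A reader might infer that haptoglobin is never scheduled during treatment, or that every subject is evaluable at just 1 of 18 or 1 of 14 visits. The V3 and V4 tests contradict both. A reader might also infer that the trial can find almost no hemolysis during treatment; the routes above do not support that. Nor does the 2.0 g/dL criterion feed a table that would show zero cases: it leads to narratives, and the 1.0 g/dL summaries are presented only if such cases occur.

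A fair point against the remedy is that an LDH rise has no threshold. If a subject's LDH values were exchangeable over time (an assumption), about half of visits would show a rise over screening by chance. At least one rise would occur in 18/19 = 95% of subjects on the 3-week schedule and 14/15 = 93% on the 4-week schedule. The LDH condition would then filter little. In addition, treatment-visit samples are drawn before the infusion, 3 or 4 weeks after the previous one, so they may miss a transient event. Both points limit what the table can show, and neither removes the need to know who was evaluable.

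**Conclusion.** The point holds for the laboratory criteria, not for hemolysis detection as a whole. Outside V3 and V4 in the first 10 patients, neither three-part criterion can be evaluated at a treatment visit from scheduled data. That affects about 60 of 70 subjects, or 40 of 50, including all pediatric subjects. Scheduled haptoglobin reaches 1.7% to 3.1% of treatment visits and 7.1% to 10.0% of post-baseline visits. The SAP has no rule for a missing haptoglobin value, so by default a subject who could not be evaluated is counted as not a case.

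The percentages assume full follow-up and everyone on one schedule. A mix of schedules falls between the figures shown, and dropout or unscheduled testing would shift them. The structural gap does not depend on those assumptions. The primary efficacy analysis is unaffected.

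**What to change.** Add to SAP 11.7.1:

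- One by-visit table, overall only, of subjects with a hemoglobin drop from screening of at least 2.0 g/dL and of at least 1.0 g/dL, each alone and together with an LDH rise from screening. Show haptoglobin at that visit as low, normal or not measured.
- The number of subjects and visits evaluable for the three-part criterion.
- A statement that any unscheduled haptoglobin result counts toward the criterion and the table, as an exception to the scheduled-visits-only rule in SAP 6.1.

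At the same time, reconcile the flowcharts: the protocol's marks hemolysis tests in the treatment period, and the SAP's does not.

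The cost is one table from data already collected. Keeping it overall avoids repeating it across the age, gender, race and region strata of SAP 11. The downside is lower specificity: many LDH rises will be chance, so a footnote should say that flagged subjects are signals for review and not hemolysis cases. No change to the testing schedule is proposed; that is a clinical decision.

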## 11.7.2. Viral Safety (Retention Samples)

In order to respond rapidly to any reports on additional viral infections, a screening blood sample from each subject included in the study is taken at the screening (initial) visit and stored at -70°C for possible future serum testing. At the closing (follow-up) visit, an additional blood sample is taken and stored up to 6 months after study end.

Statistical Analysis Plan

any subject, data will be listed only.

Version Final 2.0

03.007A.02

The analysis of viral safety samples will be decided on a case-by-case basis depending on the need for further data investigations for a subject. If viral safety samples are analyzed for Statistical Analysis Plan

Version Final 2.0

## **12.** INTERIM ANALYSES

No interim analysis of data from this trial is planned.

# 13. CHANGE FROM ANALYSIS PLANNED IN PROTOCOL

## 13.1.1. Specific IgG Trough PK Set

Specific IgG Trough PK Set was added to the definition of PK Sets to distinguish between trough concentration for Specific IgG measured at central lab unlike trough concentrations for total IgG and IgG subtypes measured at local labs.

## 13.1.2. Dense PK Subset

The protocol definition "The Dense PK Set includes all subjects following the principles of the SAF for whom at least 1 concentration of total IgGs [...]" was adjusted to "The Dense PK Set includes all subjects who received all planned doses and for whom at least 1 concentration of total IgGs [...]".

## 13.1.3. Rate of Any Infections

According to the protocol: The point estimate will be the total number of infections in all subjects divided by the total duration expressed in years of the observation period of all subjects. This is specified in the SAP "The annual rate per subject will be the total number of infections of the subject divided by the total duration expressed in years of the observation period of the subject"

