10.6 Secondary Efficacy Analyses

The following secondary endpoints will be summarized descriptively:

- IgG trough levels (total IgG) before each infusion will be presented in tabulated statistical summaries of the raw data and absolute changes from baseline values by infusion schedule and overall (evaluation of IgG trough levels will include the calculation of the proportion of subjects who failed to meet the target level of ≥5 g/L).
- Rate of any infections: The annual rate of infection will be calculated as the mean number of all infections (serious plus nonserious) per subject-year. The point estimate will be the total number of infections in all subjects divided by the total duration expressed in years of the observation period of all subjects.
- Rate of nonserious infections: The annual rate of nonserious infection will be calculated as the mean number of nonserious infections per subject-year. The point estimate will be the total number of nonserious infections in all subjects

divided by the total duration expressed in years of the observation period of all subjects.

- Time to resolution of infections will be calculated as infection stop date infection start date + 1. The presentation will be done by infusion schedule and overall and will include the frequencies of number of days until the resolution of infection. Kaplan-Meier plots will be generated for time to resolution of infection by infusion schedule and overall.
- Antibiotic treatment information will be collected via the subject diary: Monthly
 rates of days on antibiotic treatment will be calculated per subject-month. The
 point estimates will be the total number of days on antibiotics in all subjects
 divided by the total duration expressed in months (of 30 days) of the observation
 period of all subjects.
- Rate of time lost from school/work due to infections and their treatment: Monthly
 rates of the number of days not able to attend school/work due to infections and
 their treatment will be calculated per subject-month. The point estimates will be
 the total number of days off school/work due to infections and their treatment in
 all subjects divided by the total duration expressed in months (of 30 days) of the
 observation period of all subjects.

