#### 8.1. PRIMARY EFFICACY ENDPOINT AND ANALYSIS

#### 8.1.1. Primary Analysis of Primary Efficacy Endpoint

The primary efficacy endpoint is the rate of acute serious bacterial infections (i.e., the mean number of acute serious bacterial infections per subject-year) and will be based on the total of all of the following events as defined by the FDA: bacteremia or sepsis, bacterial meningitis, osteomyelitis/septic arthritis, bacterial pneumonia, and visceral abscess.

Serious bacterial infections are identified by the following criteria:

- Any AE leading to the following MedDRA PTs: sepsis, bacterial sepsis, bacteremia, meningitis bacterial, osteomyelitis bacterial, arthritis bacterial, pneumonia bacterial, abdominal abscess.

- All AEs leading to any other PT are reviewed by the sponsor for a possible relationship to the primary endpoint (e.g. AEs including one of the following words: bacteremia, sepsis, meningitis, osteomyelitis, arthritis, pneumonia, and abscess). Identified AEs possibly related to the primary endpoint are queried to the investigator to clarify if the AE fulfils the FDA criteria for acute serious bacterial infections. The investigator transfers his decision to the eCRF (AE term).

The date of onset of an episode of acute serious bacterial infections is the day the diagnosis made.

For each subject, the study duration (days) will be calculated as:

(date of last visit) – (date of first infusion) + 1

The number of subject years will be calculated by summing the total subject days and dividing by 365. An estimate of the acute serious bacterial infection rate for BT595 will be obtained by dividing the total number of acute serious bacterial infections by the total number of subject years.

Any intra-subjects correlations of acute serious bacterial infections are not considered to follow a conservative approach for the infection rates.

For the primary efficacy analysis, the acute serious bacterial infection rate for BT595 and the upper 1-sided 99% CI will be estimated by using a Poisson model accounting for the length of the observation period per subject.

A generalized linear model assuming the Poisson distribution for the number of acute serious bacterial infections with the logarithm as link function will be used. The Poisson model will include the natural logarithm of the length of the observation period in years as an offset to account for the (possibly) different lengths of the observation periods per subject.

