#### 8.2.2. Rate of Any Infections

Infections are identified by the following criteria:

- Any AE leading to the MedDRA SOC "infections and infestation".
- All AEs leading to any other SOC are reviewed by the sponsor for possible relation to an infection (e.g. pyrexia leading to SOC General disorders and administration site conditions). Identified AEs possibly related to this endpoint are queried to the investigator. The investigator transfers his decision to the eCRF (AE term).

The annual rate of infections will be calculated as the mean number of all infections (serious plus nonserious) per subject-year as described in Section 8.1.1. The annual rate per subject will be the total number of infections of the subject divided by the total duration expressed in years of the observation period of the subject. Summaries will be as for a continuous variable and by categorizing the number of any infections per subject according to the following categories:

- 0
- 1
- 2
- 3 to <5
- 5 to <10
- ≥10

The annual rate of days with infections per subject will be the total number of days with infections of the subject divided by the total duration expressed in years of the observation period of the subject.

Frequency tables presenting the number (%) of subjects with infections, the number of days with any infections and the total number of infections will be done.

Tables will also be stratified by season (spring, summer, autumn, winter) using the calendar whereas e.g. spring starts on 01Mar.

In addition, summaries will be done for the subgroup of subjects that did not receive treatment for the full period of time, either by missing an infusion or discontinuing the study.

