#### 8.2.3. Rate of Nonserious Infections

The annual rate of nonserious infections will be calculated as the mean number of nonserious infections per subject-year as described in Section 8.1.1. The annual rate per subject will be the total number of nonserious infections of the subject divided by the total duration expressed in years of the observation period of the subject. Summaries will be as for a continuous variable and by categorizing the number of any nonserious infections per subject according to the following categories:

- 0
- 1
- 2

- 3 to < 5
- 5 to <10
- ≥10

The annual rate of days with nonserious infections per subject will be the total number of days with nonserious infections of the subject divided by the total duration expressed in years of the observation period of the subject.

Frequency tables presenting the number (%) of subjects with infections, the number (%) of days with any infections and the total number (%) of infections will be done.

In addition, summaries will be done for the subgroup of subjects that did not receive treatment for the full period of time, either by missing an infusion or discontinuing the study.

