#### 8.2.5. Antibiotic Treatment Information

Monthly rates of days on concomitant antibiotic treatment will be calculated per subject-month. The monthly rate per subject will be the total number of days on antibiotics of the subject divided by the total duration expressed in months (of 30 days) of the observation period of the subject. For the imputation rules of incomplete start/stop dates refer to Section 6.3. Summaries will be as for a continuous variable.

Annual rates of days on concomitant antibiotic treatment will be calculated per subject-year. The annual rate per subject will be the total number of days on antibiotics of the subject divided by the total duration expressed in years (of 365 days) of the observation period of the subject. For the imputation rules of incomplete start/stop dates refer to Section 6.23.

Summaries will be as for a continuous variable and also by categorizing the number of days on antibiotic treatment according to the following categories:

- 0
- >0 to <7
- 7 to <14
- 14 to <21
- 21 to <35
- 35 to <70
- >=70

Summaries will be done for the number of subjects requiring treatment with antibiotics and the number of days on antibiotic treatment.

In addition, the number and percentage of subjects taking concomitant antibiotic medications will be summarized by ATC Levels 2, 3 and 4.

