#### 8.2.7. Hospitalization / Hospitalization due to Infection

Monthly rates of the number of days of hospitalization (any hospitalization/ hospitalization due to infection) will be calculated per subject-month. The monthly rate will be the total number of days in hospital of the subject divided by the total duration expressed in months (of 30 days) of the observation period of the subject. Summaries will be as for a continuous variable.

Annual rates of the number of days of hospitalization (any hospitalization/ hospitalization due to infection) will be calculated per subject-year. The annual rate will be the total number of days in hospital of the subject divided by the total duration expressed in years (of 365 days) of the observation period of the subject.

Summaries will be as for a continuous variable and also by categorizing the number of days of hospitalization according to the following categories:

- 0
- >0 to <7
- 7 to <14
- 14 to <21
- 21 to <35
- 35 to <70
- >=70

Summaries will be done for number of subjects (%) with hospitalization and the number of days of hospitalization.

Separate calculation will be generated for hospitalization due to serious bacterial infections (SBI).

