#### 8.2.8. Fever Episodes

Fever is defined as a body temperature  $\geq 38^{\circ}$ C ( $\geq 100.4^{\circ}$ F). Fever, which recurs after  $\geq 3$  days without fever will be counted as a new fever episode. The number of days of fever for a given fever episode is defined as the number of days from the first day of a body temperature  $\geq 38^{\circ}$ C ( $\geq 100.4^{\circ}$ F) to the last day with a body temperature  $\geq 38^{\circ}$ C ( $\geq 100.4^{\circ}$ F) to the last day with a body temperature  $\geq 38^{\circ}$ C ( $\geq 100.4^{\circ}$ F) including gaps between days with fever <3 days.

The number of days with episodes of fever will be calculated as the mean number of fever episodes per subject-year as described in Section 8.1.1. The annual rate per subject will be the total number of days with episodes of fever of the subject divided by the total duration expressed in years of the observation period of the subject.

Summaries will be as for a continuous variable and also by categorizing the data according to the categories:

- 0
- 1 to <=2
- 3 to <5
- 5 to <8
- 8 to <10
- 10 to <14
- ≥14

Summaries will be done for number (%) of subjects with fever episodes and total number of days with episodes of fever.

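### SAP 8.2.5 to 8.2.7 drop the protocol's pooled rate for antibiotic, school/work and hospital days, and for infections and fever the SAP does not say which rate is the point estimate.

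*SAP*

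**What the plan says.** Protocol 10.6 uses one recipe for all the secondary rates. For any infections: "The point estimate will be the total number of infections in all subjects divided by the total duration expressed in years", with the duration also totalled over all subjects. Nonserious infections and fever days follow the same form per year. Antibiotic days, school/work days lost and hospital days follow it per 30-day month.

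The SAP treats these endpoints in two ways.

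- **Antibiotic days, school/work days lost, hospital days (SAP 8.2.5 to 8.2.7).** Only a subject-level rate is defined, in monthly and annual versions. For antibiotics: "The annual rate per subject will be the total number of days on antibiotics of the subject divided by the total duration" for that subject. For hospital stays: "The monthly rate will be the total number of days in hospital of the subject divided by the total duration expressed in months". None of the three sections refers to 8.1.1. The rates are summarised as continuous variables, which under SAP 6.1 means arithmetic mean, SD, median, minimum and maximum.
- **Any infections, nonserious infections, fever (SAP 8.2.2, 8.2.3, 8.2.8).** The rate is first given as the "mean number of all infections (serious plus nonserious) per subject-year as described in Section 8.1.1", the "mean number of nonserious infections per subject-year as described in Section 8.1.1" and the "mean number of fever episodes per subject-year as described in Section 8.1.1". Section 8.1.1 is pooled: it works by "dividing the total number of acute serious bacterial infections by the total number of subject years". Each section then adds a subject-level rate.

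SAP 13.1.3, 13.1.4 and 13.1.6 to 13.1.9 record the subject-level rate as the departure from the protocol for all six endpoints. For any infections, 13.1.3 reads: "The annual rate per subject will be the total number of infections of the subject divided by the total duration expressed in years", counted for that subject alone. These entries give no reason, although other entries do (13.1.12, for example, cites regulatory advice).

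**The concern.** The pooled rate weights each subject by time observed. The mean of subject-level rates weights everyone equally, so a few weeks of follow-up count as much as a full year. One dose admits a subject to the FAS (SAP 5.3), the observation period is simply first infusion to last visit (SAP 8.1.1), and no minimum or weighting is stated. One early leaver with an event can therefore move the mean visibly.

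Two things are at stake. For three endpoints, a programmer following the SAP would not produce the quantity that the protocol defines. For the other three, two figures could each be reported as the annual rate. SAP 2.2 plans to set the efficacy results beside historical product studies and the literature, and that requires knowing which rate is being quoted.

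**Working it through.** The documents give no figure for any secondary rate, so there is none to reproduce.

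**Inputs from the documents.** About 70 enrolled for at least 50 evaluable (Protocol 10.9, SAP 3.5). Full follow-up runs to about day 379 (3-week) or 393 (4-week) (flowchart); the midpoint is 386. Event rates, drop-out times and dispersion are not given and are assumptions below.

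**1. The two estimators.** With d events or days over time t for each subject, pooled = Σd / Σt and mean of rates = (1/n) Σ(d/t). They agree when every t is equal. With 69 completers at 386 days and one subject at 21 days, the short subject's weight is 1/70 = 1.4% in the mean and 21/(69×386 + 21) = 21/26,655 = 0.08% in the pooled rate.

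**2. Antibiotic days.** Assume one subject leaves on day 21 with 7 antibiotic days.
- Own rate: 7/21 × 365 = 121.7 days/year.
- Contribution to the 70-subject mean: 121.7/70 = 1.74 days/year.
- Contribution to the pooled rate: 7/(70×386/365) = 0.09 days/year (0.10 if this subject's time is counted as 21 days).

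The relative shift depends on the assumed rate in the other 69:

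| Others (days/year) | Mean of rates | Pooled |
|---|---|---|
| 10 | 11.60 (+16%) | 10.09 (+0.9%) |
| 20 | 21.45 (+7%) | 20.08 (+0.4%) |
| 40 | 41.17 (+3%) | 40.06 (+0.2%) |

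**3. Hospital days.** Assume the others average 0.1 day/month over 393 days, and one subject leaves on day 21 with 10 hospital days (own rate 10/(21/30) = 14.29 per month). Mean = (69×0.1 + 14.29)/70 = 0.303; pooled = 0.111. With 0.5 day/month in the others the figures are 0.697 and 0.511; with 2 day/month, 2.18 and 2.01.

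**4. Infections (the ambiguous group).** Assume 3/year in the others over 393 days, and one leaver with one infection.
- Day 21: mean = (69×3 + 365/21)/70 = 3.21 (+6.8%); pooled = (69×3×393/365 + 1)/((69×393 + 21)/365) = 3.01 (+0.4%).
- Day 7: mean 3.70 (+23%), pooled 3.01.
- Day 90: mean 3.02 (+0.5%), pooled 3.00.

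**5. Do they estimate the same thing?** Let 20 of 70 drop out uniformly over days 21 to 365 (average 193), with 50 completing 393 days. If drop-out is unrelated to infection, both estimators average 3.00. If the drop-outs have 1.5 times the rate:
- pooled ≈ 3 × (50×393 + 1.5×20×193)/(50×393 + 20×193) = 3 × 25,440/23,510 = 3.25
- mean = 3 × (50 + 1.5×20)/70 = 3.43

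**6. Precision.** With count variance λt + αλ²t², Var(mean) = Σ(λ/t + αλ²)/n² and Var(pooled) = Σ(λt + αλ²t²)/(Σt)². For 70 subjects, 20 drop-outs uniform from 21 days to 1 year, 386 days for the rest and λ = 3/year, the ratio Var(mean)/Var(pooled) is:

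| Dispersion α | 0 | 0.3 | 1 | 2 | 4 |
|---|---|---|---|---|---|
| Ratio | 1.40 | 1.17 | 1.03 | 0.98 | 0.95 |

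At 5/year the ratio is already 0.99 at α = 1. The direction depends on a dispersion that the documents do not give.

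**The case against.** A reader of Section 13 might infer that the SAP replaces the pooled rate for every secondary endpoint. The documents do not support that: 8.2.2, 8.2.3 and 8.2.8 still route the calculation through 8.1.1, which is pooled, and the subject-level rate follows as an addition. A reader might also infer that the mean of rates is always less precise. Step 6 shows that this fails under strong between-subject heterogeneity.

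The rest of the defence is fair and mostly stands. A mean of subject rates is a legitimate descriptive quantity. Protocol 10.6 makes these endpoints descriptive, with no test or decision rule. The changes are listed openly. Medians and extremes are shown, so an outlying early leaver would be noticed. SAP 8.2.6 tabulates total subject days and days lost, so the pooled school/work rate can be rebuilt from the table. The same may be possible for antibiotics and hospital stays if totals are shown, since 8.2.5 and 8.2.7 summarise days and 11.1 summarises exposure. The examples in steps 2 to 4 are chosen early drop-outs, and departure around day 90 matters little.

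The defence does not fully cover the three endpoints affected most. The separate summaries for subjects who missed an infusion or discontinued appear in 8.2.2 and 8.2.3, not in 8.2.5 to 8.2.7. Being able to rebuild a rate is also not the same as specifying it.

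**Conclusion.** The point holds in two parts. For antibiotic days, school/work days and hospital days, the SAP as written does not yield the protocol's point estimate, and no reason is given. For any infections, nonserious infections and fever, the pooled rate survives by cross-reference, but Section 13 presents the subject-level rate as the change, so the point estimate is ambiguous.

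Under the stated assumptions, one leaver on day 21 shifts the mean of rates by roughly 3% to 16% for antibiotic days, against under 1% for the pooled rate. For a rare outcome such as hospital days the mean can nearly triple (0.303 against 0.111). Drop-out unrelated to infection produces no systematic difference; related drop-out does (3.43 against 3.25 in the example). No general claim about precision is warranted. The primary Poisson analysis with its log-time offset is unaffected. Priority is low.

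**What to change.** - **SAP 8.2.5 to 8.2.7:** restore the protocol's pooled rate (total days over total observation time) as the point estimate.
- **SAP 8.2.2, 8.2.3 and 8.2.8:** state explicitly that the pooled rate from 8.1.1 is the point estimate.
- **SAP 13.1.3, 13.1.4 and 13.1.6 to 13.1.9:** reword to match, recording the subject-level rates as additions.
- **All six endpoints:** keep the subject-level distribution, labelled as supplementary.

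A confidence interval for the pooled rates is optional, since Protocol 10.6 prescribes none for them specifically. The cost is SAP wording and one extra row per table; no new data are needed.
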